6.1.4. Handling of Dropouts or Missing Data

The Daily Pain and Sleep Interference Diary is to be completed within 14 days of the 12-month visit. The average 24-hour pain score for a visit will be considered as missing if fewer than 5 of 7 days of Daily Pain and Sleep Interference Diary entries are provided. Sensitivity analyses for the mean change in the average 24-hour pain score will include the following imputation approaches for missing values at 3, 6, 9, or 12 months. It is important to note that over-stratification may result when the total list of pre-specified factors is considered. Under this scenario, the least represented factor will be removed and the imputation will be re-run. This process will be followed until the imputed dataset is complete.

- Multiple imputation: Each missing pain score will be imputed ten times to generate ten imputed complete data sets based on the Markov Chain Monte Carlo (MCMC) method with baseline pain score, 3-month and 6-month pain score, and categorical covariates of baseline use of gabapentin and/or pregabalin, baseline HbA1c, gender, and age. The imputed score will be rounded to the first decimal point. The results of the ten tests from the continuous Repeated Measures Model using these data will be combined.
- Mean of the other group (MOTH)¹ as follows:
 - 1. For a subject with a missing 3-month or 6-month average 24-hour pain score, identify the subject's following baseline characteristics:
 - Study treatment group
 - Baseline use of gabapentin and/or pregabalin.
 - Baseline average 24-hour pain score (< median or ≥ median)
 - HbA1c (< median or ≥ median)
 - Gender (male or female)
 - Age (<65 years and ≥ 65 years).

The median subgroups will be based on the median of ITT subjects in the VMDN-003 study such that VMDN-003b subjects remain in the same subgroups across studies.

2. The missing 3-month, 6-month, 9-month, or 12-month average 24-hour pain score will be imputed by using the mean average 24-hour pain score obtained at the same time point of those subjects in the other treatment group who match the subject's baseline characteristics. For example, for the missing pain scores of the VM202 subjects, the mean pain scores of the placebo subjects within the same

AD-ST-33.05 Effective date: 22-Jan-2018

covariate groups will be used to impute the missing pain scores.

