- The baseline characteristics will be re-examined for appropriateness and may be re-categorized (due to small sample size) before unblinding the study.
- 4. The imputed score will be rounded to the first decimal point. The imputed scores will be included in the continuous Repeated Measures Model analysis.

Sensitivity analyses for the percentage of subjects with a reduction in the average 24-hour pain score of at least 50% will include the following imputation approaches for missing values at 3 or 6 months.

- Imputed average 24-hour pain scores at 3, 6, 9, and 12 months from the multiply-imputed pain score datasets described above. The results of the ten tests from the categorical Repeated Measures Model will be combined.
- Missing pain score will be imputed from the MOTH-imputed dataset described above and the categorical Repeated Measures Model will be used for the data analyses.
- Multiple imputation for the missing responder outcomes, 1 (Yes) or 0 (No), by fully
 conditional specification logistic regression method: each missing responder outcome
 will be imputed ten times to generate ten imputed complete data sets using a logistic
 regression model with baseline use of gabapentin and/or pregabalin, and categorical
 baseline HbA1c, gender, and age as covariates. The results of the ten tests from the
 categorical Repeated Measures Model will be combined.

Steps to generate the MMRM analysis are presented below; different options will be used depending on the exact model being run. First the proc mixed code in section 8.1 will be run within each imputation dataset. Least square means, differences between treatments, and p-values will be combined using the following MIANALYZE code.

Proc Mianalyze data=[LS Mean/Difference/p-value dataset from proc mixed];

by avisitn trtn; modeleffects estimate; stderr;

Run:

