
[3] P value for testing difference (VM202 minus Placebo) in mean change from baseline from is zero.

SOURCE: Listing 16.2.6.1

Programming note: Check convergence per Section 8.1 of the SAP. Other variance-covariance structures selected from among compound symmetry, Toeplitz, and autoregressive (1) options may be substituted if convergence problems arise. Update footnote accordingly.

Table 14.2.1.2.1 Summary of Change from Baseline in Average 24-hour Pain Score Multiple Imputation ITT Population

Same shell as 14.2.1.1.1, add the following to footnote "Each missing pain score was imputed ten times to generate ten imputed complete data sets based on the Markov Chain Monte Carlo (MCMC) method with categorical covariates of baseline use of gabapentin/pregabalin, baseline hbA1c, gender, race, and age."

Table 14.2.1.2.2

Mean Change from Baseline in Average 24-hour Pain Score by Study Visit and Treatment
Tabulation of Fitted Summary Statistics from MMRM using Multiple Imputation
ITT Population

Same shell as 14.2.1.1.5, add the following to footnote [1] "Each missing pain score was imputed ten times to generate ten imputed complete data sets based on the Markov Chain Monte Carlo (MCMC) method with categorical covariates of baseline use of gabapentin/pregabalin, baseline hbA1c, gender, race, and age"

Table 14.2.1.3.1 Summary of Change from Baseline in Average 24-hour Pain Score MOTH Imputation ITT Population

Same shell as 14.2.1.1.1, add the following to footnote "Each missing 3-month or 6-month average 24-hour pain score was imputed using the mean average 24-hour pain score obtained at the same time point of those subjects in the other treatment group who match the subject's baseline characteristics. Characteristics considered are baseline use of gabapentin/pregabalin, baseline average 24 hour pain score (less than median; more than or equal to median), HbA1c (less than median; more than or equal to median), gender, race (white; non-white), and age (less than median; more than or equal to median)."

Table 14.2.1.3.2

[figure not shown]
Mean Change from Baseline in Average 24-hour Pain Score by Study Visit and Treatment Tabulation of Fitted Summary Statistics from MMRM using MOTH Imputation ITT Population

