Same shell as 14.2.1.10.2. Add Age (less than 65 years; more than or equal to 65 years) as a covariate in the model and in footnote [1].

Table 14.2.1.11

Summary of Change from Baseline in Average 24-hour Pain Score by Baseline Use of Gabapentin and/or Pregabalin ITT Population

Same shell as 14.2.1.1.1, add a row at the top of table reading "Group: Gabapentin and/or Pregabalin Use". Once all records from group are summarized, update row text for No Gabapentin and/or Pregabalin Use and start table on a new page.

Table 14.2.1.12

Summary of Change from Baseline in Average 24-hour Pain Score by Study Center **ITT Population**

Same shell as 14.2.1.1.1, add a row at the top of table reading "Group: Study Center" Once all records from group are summarized, update row text for the next study center and start table on a new page. Add 16.2.1.1 to SOURCE.

Table 14 2 1 13

Summary of Change from Baseline in Average 24-hour Pain Score by VMDN-003 Protocol Version

ITT Population

Same shell as 14.2.1.1.1.1, add a row at the top of table reading "Group: Protocol Version C". Once all records from group are summarized, update row text for

AD-ST-33.05 Effective date: 22-Jan-2018

Version A 07-Aug-2019 | AD-PR-109.01 Effective date: 26-Jun-2017 Page 45 of 93

[figure not shown]
the next group and start table on a new page. Groups will be: C, D, and E. Add 16.2.1.1 to SOURCE.

Table 14.2.1.14

Mean Change from Baseline in Average 24-hour Pain Score by Study Visit and Treatment Adjusted for Covariates
Tabulation of Fitted Summary Statistics from MMRM

ITT Population

Same shell as 14.2.1.1.1.2. Add all 4 covariates (HbA1c, Gender, and Age (with 65 years as the cutoff) as covariates in the model and in footnote [1]. Add 16.2.4

Helixmith Co., Ltd. Protocol VMDN-003b

[figure not shown]
CONFIDENTIAL

Page x of y <Version>

Table 14.2.2.1
Summary of Subjects with at least a 50% Reduction from Baseline in the Average 24-hour Pain Score ITT Population

Study Visit Statistic	Placebo (N=XX)	VM202 (N=XX)
Day 90 Number of Responders	XX (XX.X%)	XX (XX.X%)
Day 180 Number of Responders	XX (XX.X%)	XX (XX.X%)
Day 270 Number of Responders	XX (XX.X%)	XX (XX.X%)
Day 365 Number of Responders	XX (XX.X%)	XX (XX.X%)

Note: Subjects with a percent change of ≤ -50% from baseline (i.e., reduction of at least 50%) will be classified as a responder at the respective visit. The baseline value is the average 24-hour pain score from the diary collected prior to Day 0. SOURCE: Listing 16.2.6.1

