Same shell as 14.2.1.2.2, add the following to footnote [1] "Each missing pain score was imputed ten times to generate ten imputed complete data sets based on the Markov Chain Monte Carlo (MCMC) method with categorical covariates of baseline use of gabapentin/pregabalin, baseline hbA1c, gender, race, and age."

Table 14.2.2.4

Analysis of Responder Rate of at least 50% Reduction from Baseline in Average 24-hour Pain Score by Study Visit and Treatment Tabulation of Fitted Summary Statistics from GLMM for Repeated Measures using MOTH Imputation

ITT Population

Same shell as 14.2.1.2.2, add the following to footnote [1] "Each missing 3-month or 6-month average 24-hour pain score was imputed using the mean average 24-hour pain score obtained at the same time point of those subjects in the other treatment group who match the subject's baseline characteristics.

Characteristics considered are baseline use of gabapentin/pregabalin, baseline average 24 hour pain score (less than median; more than or equal to median), gender, race (white: non-white), and age (less than 65 years: more than or equal to 65 years)."

Table 14.2.2.5

Analysis of Responder Rate of at least 50% Reduction from Baseline in Average 24-hour Pain Score by Study Visit and Treatment Tabulation of Fitted Summary Statistics from GLMM for Repeated Measures using Fully Conditional Logistic Regression Imputation ITT Population

Same shell as 14.2.1.2.2, add the following to footnote [1] "Each missing responder outcome will be imputed ten times to generate ten imputed complete data sets using a logistic regression model with baseline use of gabapentin and/or pregabalin, and categorical baseline HbA1c, gender, race, and age as covariates."

Table 14.2.2.6

Analysis of Responder Rate of at least 50% Reduction from Baseline in Average 24-hour Pain Score by Study Visit and Treatment
Tabulation of Fitted Summary Statistics from GLMM for Repeated Measures
ITT Population Excluding Scores Influenced by Prohibited Concomitant Medications

Same shell as 14.2.1.2.2

Table 14 2 2 7 1

Summary of Subjects with at least 50% Reduction from Baseline in the Average 24-hour Pain Score by Hb1Ac

Same shell as 14.2.2.1, add a row at the top of table reading "Group: HbA1c < Median". Once all records from group are summarized, update row text for the next group and start table on a new page. Groups will be: < Median and >= Median. Populate Median with actual value.

[figure not shown]

Table 14.2.2.7.2

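### SAP 6.1.4 and the imputation table notes give conflicting factors and visits for the missing-data sensitivity analyses of pain, including at Day 365

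*SAP*

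**What the plan says.** **SAP 6.1.4.** None of its imputation methods uses race, and all of them use HbA1c.

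- The MCMC multiple imputation uses baseline, 3-month and 6-month pain scores and "categorical covariates of baseline use of gabapentin and/or pregabalin, baseline HbA1c, gender, and age".
- MOTH matches on gabapentin/pregabalin use, baseline pain, HbA1c, gender and age cut at 65, with median splits taken from the VMDN-003 ITT subjects.
- The logistic (FCS) imputation of responder status uses gabapentin/pregabalin use, HbA1c, gender and age.

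On visits, the pain-score lead-in and MOTH step 2 cover 3, 6, 9 and 12 months. MOTH step 1 begins "For a subject with a missing 3-month or 6-month average 24-hour pain score". The responder lead-in speaks of the "following imputation approaches for missing values at 3 or 6 months", yet the first bullet beneath it covers all four visits. The responder analyses are to reuse the imputed pain-score datasets already described.

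**SAP 14.2, table notes.**

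- Multiple imputation (Tables 14.2.1.2.1, 14.2.1.2.2 and 14.2.2.3): "categorical covariates of baseline use of gabapentin/pregabalin, baseline hbA1c, gender, race, and age". No pain scores are listed as predictors.
- MOTH, mean change (Tables 14.2.1.3.1 and 14.2.1.3.2): "Each missing 3-month or 6-month average 24-hour pain score was imputed using the mean average 24-hour pain score obtained at the same time point". The matching factors include "race (white; non-white), and age (less than median; more than or equal to median".
- MOTH, responders (Table 14.2.2.4): again 3 and 6 months, with HbA1c absent and "race (white: non-white), and age (less than 65 years: more than or equal to 65 years".
- FCS (Table 14.2.2.5): race added.

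**Protocol 5.6.3** says that missing values will not be imputed. SAP section 10 reports changes from the planned analysis as not applicable.

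**The concern.** These notes state which scores are filled and whose data fill them, so they are analysis rules. Under Protocol 3.4.3, subjects consent at or after the Day 270 assessments. Day 365 is therefore the only diary collected after consent, and both secondary pain-change endpoints end there. A missing-data sensitivity analysis in this extension exists mainly for that score.

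The 3- and 6-month wording would leave missing Day 365 scores unfilled in MOTH. The MCMC predictor list, as written, omits the Day 270 score, which is the one closest in time to Day 365. With several factor lists in one SAP, two programmers could build different imputed datasets and each be following the text. SAP section 13 treats footnote edits as cosmetic changes that need no SAP modification, so the choice could be made without a record.

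**Working it through.** The documents state no sample size, arm size or expected missingness for this study, so there is no plan figure to reproduce. The check is a comparison of texts and one illustrative count.

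**1. Factors**

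| Source | Race | HbA1c | Age |
|---|---|---|---|
| 6.1.4 MCMC | no | yes | categorical, cut not stated |
| 6.1.4 MOTH | no | yes | 65 years |
| 6.1.4 FCS | no | yes | categorical, cut not stated |
| Notes 14.2.1.2.1, 14.2.1.2.2, 14.2.2.3 (MI) | yes | yes | cut not stated |
| Notes 14.2.1.3.1, 14.2.1.3.2 (MOTH) | yes | yes | median |
| Note 14.2.2.4 (MOTH) | yes | no | 65 years |
| Note 14.2.2.5 (FCS) | yes | yes | cut not stated |

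MOTH alone therefore has three donor rules: 6.1.4, the 14.2.1.3.x notes, and the 14.2.2.4 note.

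**2. Visits**

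| 3, 6, 9 and 12 months | 3 and 6 months only | No visit limit |
|---|---|---|
| 6.1.4 pain-score lead-in | 6.1.4 MOTH step 1 | MI notes |
| 6.1.4 MOTH step 2 | 6.1.4 responder lead-in | FCS note |
| 6.1.4 first responder bullet | All three MOTH notes | |

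The conflict lies inside 6.1.4 as well as between 6.1.4 and the notes, so it is not enough to say that 6.1.4 governs.

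**3. MOTH cell counts.** Treatment group only determines which arm supplies the donors. The rest are binary factors.

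- 6.1.4: five factors, 2^5 = 32 cells.
- Notes 14.2.1.3.1 and 14.2.1.3.2: six factors, 2^6 = 64 cells.
- Note 14.2.2.4: five factors, 2^5 = 32 cells, but a different 32 (race in, HbA1c out).

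**4. Chance that a subject's cell has no donor.** The number of donors n is an assumption. With K equal cells the chance is (1 − 1/K)^n. With unequal cells of probability p it is the sum over cells of p(1 − p)^n. For the unequal case I assume two factors at 70/30, race (where used) at 80/20, and the rest at 50/50.

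| n | Equal, 32 cells | Equal, 64 cells | Skewed, 5 factors | Skewed, 6 factors |
|---|---|---|---|---|
| 30 | 0.386 | 0.623 | 0.327 | 0.476 |
| 50 | 0.204 | 0.455 | 0.183 | 0.327 |
| 100 | 0.042 | 0.207 | 0.059 | 0.165 |

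Skew lowers five of the six equal-cell figures and raises one (32 cells, n = 100). The six-factor rule has the higher chance of no donor in every row.

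**The case against.** The best defence is that the operative sentences already settle Day 365. MOTH step 1 only identifies a subject's characteristics. Step 2 does the imputing, and it names 9 and 12 months. The MI and FCS notes have no visit limit. A reader might infer from the notes that Day 365 is never imputed, and the documents do not support that: the restriction touches MOTH only, and only if step 1 and the notes are allowed to override step 2. What stands is that step 1, the responder lead-in and three table notes all say otherwise.

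A reader might also infer that the mean-change and responder results will come from different imputed data. Section 6.1.4 says that the responder analyses reuse the same datasets, so a differing footnote does not by itself create a second one. The missing HbA1c in the 14.2.2.4 note may be a copying slip or a loss in reading the PDF, although the sentence reads as complete. Even so, a note that misdescribes its dataset has to be corrected.

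In a joint MCMC model, any score being imputed is itself in the model, so a programmer might well include the 9-month score. The SAP's list does not say so.

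Section 6.1.4 allows factors to be dropped when cells are too sparse and recategorised before unblinding. That covers sparse cells but not the addition of race. It also limits what the cell counts show, because one unmatched subject is enough to trigger factor removal. With an assumed 10 missing subjects, equal cells and no-donor chance q, treating subjects as independent, 1 − (1 − q)^10 gives 99% against more than 99.9% (n = 30), 90% against 99.8% (n = 50) and 35% against 90% (n = 100). At the smaller sizes both rules nearly always trigger it.

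**Conclusion.** The conflict is in the text and should be resolved before unblinding. The factor lists differ on race in all seven notes, on the age cut in two, and on HbA1c in one. The visit rule differs within 6.1.4 and in the three MOTH notes. On the 3- and 6-month wording, MOTH leaves missing Day 365 scores unfilled and its Day 365 result largely repeats the main model.

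The reach is limited. These are sensitivity analyses of secondary endpoints in a study without a power calculation, and neither the adverse-event primary endpoint nor the main repeated-measures model is affected. No effect on any Day 365 estimate has been shown. The cell-count figures illustrate direction only and rest on assumed donor numbers and factor frequencies. The 64-cell rule belongs to the 14.2.1.3.x notes and not to 14.2.2.4.

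Two nearby slips are minor wording corrections, not imputation rules. The covariate-adjusted tables say "Add all 4 covariates (HbA1c, Gender, and Age (with 65 years as the cutoff" and so name three covariates, and SAP 8.2 writes the upper age group as above 65, where other places use 65 or more.

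**What to change.** Before unblinding:

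1. State one factor list and one age cut in SAP 6.1.4 and copy them into all seven notes. Its present list will serve: gabapentin/pregabalin use, baseline pain, HbA1c at the VMDN-003 median, gender, and age below 65 against 65 or more. The documents give no reason for or against race, so if race is wanted, it should be added everywhere with a rationale. The FCS model in 6.1.4 does not name baseline pain; say whether that is intended.
2. In MOTH step 1, the responder lead-in and the three MOTH notes, say that missing 3-, 6-, 9- and 12-month scores are imputed.
3. Add the 9-month score to the MCMC predictors in 6.1.4, and list the pain-score predictors in the MI notes.
4. Record the imputation analyses in SAP section 10 as a departure from Protocol 5.6.3. Aligning the notes does not remove that conflict.
5. Separately, correct the count of covariates and the age boundary in 8.2.

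The cost is SAP and shell wording. No new data are needed.

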3.5. Method of Assigning Subjects to Treatment Groups

In the safety outputs, subjects will be analyzed using the treatment they received in the VMDN-003 study. Subjects will be analyzed according to treatment received, regardless of original treatment assigned.

In the efficacy outputs, subjects will be analyzed according to randomized treatment on the VMDN-003 study.

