4.1. Introduction

Data processing, tabulation of descriptive statistics, calculation of inferential statistics, and graphical representations be performed primarily using SAS (release 9.4 or higher). If the use of other software is warranted, the final statistical methodology report will detail what software was used for what purposes.

Continuous (quantitative) variable summaries will include the number of subjects (n) with non-missing values, mean, standard deviation (SD), median, minimum, and maximum. Other statistics such as coefficient of variation (%CV), quartiles, confidence intervals (CIs), and number of missing values may be added as appropriate.

Categorical (qualitative) variable summaries will include the frequency and percentage of subjects who are in the particular category or each possible value. In general, the denominator for the percentage calculation will be based upon the total number of subjects in the study population within each treatment group, unless otherwise specified. The denominator for by-visit displays will be the number of subjects in the relevant study population with non-missing data at each visit.

The minimum and maximum will be reported with the same degree of precision (ie, the same number of decimal places) as the observed data, unless that precision exceeds two decimal places. If the precision does exceed two decimal places, the minimum and maximum will be reported with two decimal places. Measures of location (mean and median) will be reported to one degree of precision more than the observed data and measures of spread (SD) will be reported to two degrees of precision more than the observed data.

Percentages will be presented to one decimal place, unless otherwise specified.

Summary tables will present results by treatment group (i.e., VM202 and Placebo) both within and across the randomization stratification factor (i.e., baseline use of gabapentin and/or pregabalin) values.

Unless otherwise indicated, all statistical tests will be conducted at the 0.05 significance level using 2-tailed tests, and P values will be reported. Corresponding 95% confidence intervals (CIs) will be presented for statistical tests.

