4.2. Interim Analysis and Data Monitoring

No interim analyses are planned.

The independent safety monitoring board (DSMB) will periodically review a limited set of unblinded tables, listings, and/or datasets, including all reported AEs, as per its responsibilities described in the DSMB Charter. The objectives of the DSMB meetings are to review the safety outcomes of the study and provide guidance to study sponsor regarding the safety of VM202. The data analyses for the DSMB meetings will be provided to the DSMB members and other participants of the DSMB meeting. For additional information, please see the DSMB Charter.

5. Analysis Populations

- The safety population (SAF) will include all subjects who sign consent for the safety
 extension study. Subjects in the analysis population will be analyzed according to the
 treatment received in the VMDN-003 study, regardless of the treatment assigned at
 randomization. Subjects that sign informed consent but screen fail will still be considered
 part of the safety population and will have their collected safety data summarized.
- The intent-to-treat (ITT) population will include all subjects who sign consent for the safety extension study and who were randomized on the VMDN-003 study. The ITT population will be the primary population used for the efficacy analyses. In such analyses, subjects will be randomized according to their randomized treatment on the VMDN-003 study.
- The modified intent-to-treat (mITT) population will include all subjects who sign consent for the safety extension study and complete the Day 365 visit.

6. General Issues for Statistical Analysis

All safety outputs will be based on the safety population and all listings will be presented by actual treatment received. All efficacy outputs will be presented by randomized treatment on the VMDN-003 study. Unless otherwise stated, table outputs will contain a placebo column and a VM202 column. Table and figure outputs based on the baseline use of gabapentin/pregabalin stratification group will also be provided.

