Table 14.2.3.2.1

Analysis of Responder Rate of at least a 20% Reduction from Baseline in Average 24-hour Pain Score by Study Visit and Treatment Tabulation of Fitted Summary Statistics from GLMM for Repeated Measures mITT Population

Study Visit Statistic [1]	Placebo (N=XX)	VM202 (N=XX)
Day 90		
n	XX	XX
LS Mean Change in Responder Rate from Baseline (SE) (95% CI for LS Mean Change in Responder Rate from Baseline)	(XX.X, XX.X)	XX.X (X.XX) (XX.X, XX.X)
LS Mean Difference from Placebo (SE) (95% CI for Difference from Placebo)		XX.X (X.XX) (XX.X, XX.X)
P value for Difference from Placebo [3]		X.XXXX
Day 180		
n	XX	XX
LS Mean Change in Responder Rate from Baseline (SE)	XX.X (X.XX)	XX.X (X.XX)
(95% CI for LS Mean Change in Responder Rate from Baseline)	(xx.x, xx.x)	(XX.X, XX.X)
LS Mean Difference from Placebo (SE)		XX.X (X.XX)
(95% CI for Difference from Placebo)		(XX.X, XX.X)
P value for Difference from Placebo [3]		X.XXXX
Continue for Day	270 and Day 365	

Abbreviation: CI = confidence interval; LS = least squares; GLMM = generalized linear mixed-effects model; SE = standard error.

Note: Subjects are summarized by randomized treatment.

The baseline value is the average 24-hour pain score from the diary collected prior to Day 0.

[1] Estimates for LS means (percent change from baseline) and accompanying 95% CIs are from a generalized linear mixed-effects model for repeated measures (GLMM) based on a logit link function. The model included treatment, visit, treatment-by-visit interaction, baseline use of gabapentin and/or pregabalin, and baseline average 24-hour pain scores as covariates. An unstructured covariance matrix was used to model the within subject correlation.

SOURCE: Listing 16.2.6.1

Programming note: Other variance-covariance structures selected from among compound symmetry, Toeplitz, and autoregressive (1) options may be substituted if convergence problems arise. Update footnotes accordingly.

Table 14.2.3.2.2

Analysis of Responder Rate of at least a 30% Reduction from Baseline in Average 24-hour Pain Score by Study Visit and Treatment Tabulation of Fitted Summary Statistics from GLMM for Repeated Measures mITT Population

Same shell as 14.2.3.2.1

Table 14.2.3.2.3

Analysis of Responder Rate of at least a 40% Reduction from Baseline in Average 24-hour Pain Score by Study Visit and Treatment Tabulation of Fitted Summary Statistics from GLMM for Repeated Measures mITT Population

Same shell as 14.2.3.2.1

Table 14.2.3.2.4

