Note: The denominator for percentage corresponds to the N in each column. N is the number of subjects in the safety population. Subjects are summarized by treatment received in the VMDN-003 study.

[1] P-value from a Cochran-Mantel-Haenszel (CMH) test (stratified by baseline use of gabapentin/pregabalin) comparing VM202 to Placebo. SOURCE: Listing 16.2.6.2

[figure not shown]
[figure not shown]

Table 14.2.5.2
Summary of Patient's Global Impression of Change (PGIC) by Gabapentin and/or Pregabalin use at Baseline mITT Population

Same shell as Table 14.2.5.1, add a row at the top of table reading "Group: Gabapentin and/or Pregabalin Use". Once all records from group are summarized, update row text to "Group: No Gabapentin and/or Pregabalin Use" and start table on a new page. Do not include the CMH test or footnote.

Helixmith Co., Ltd. Protocol VMDN-003b

CONFIDENTIAL

Page x of y <Version>

Table 14.3.1.1.1 Summary of Treatment Emergent Adverse Events Safety Population

Category	Placebo (N=XX) n (%)	VM202 (N=XX) n (%)	Overall (N=XX) n (%)
Subjects with at least one TEAE	XX (XX.X%)	XX (XX.X%)	XX (XX.X%)
Subjects with at least one TEAE related to study medication	XX (XX.X%)	XX (XX.X%)	XX (XX.X%)
Subjects with at least one TEAE related to injection procedure	XX (XX.X%)	XX (XX.X%)	XX (XX.X%)
Subjects with at least one TEAE leading to discontinuation	XX (XX.X%)	XX (XX.X%)	XX (XX.X%)
Subjects with at least one TEAE leading to death	XX (XX.X%)	XX (XX.X%)	XX (XX.X%)
Subjects with at least one SAE	XX (XX.X%)	XX (XX.X%)	XX (XX.X%)

Abbreviations: PT = Preferred Term; SOC = System Organ Class; TEAE = Treatment emergent adverse event; SAE = Serious treatment emergent adverse event; N = Number of subjects in the safety population; n = Number of subjects with events.

Note: The denominator for percentage corresponds to the N in each column. Subjects are summarized by treatment received in the VMDN-003 study. AEs were coded using MedDRA version 21.0. A TEAE is any AE that occurs after the last visit in the VMDN-003 study and pre-existing medical conditions that worsen following the last visit in the VMDN-003 study.

SOURCE: Listing 16.2.7.1

[figure not shown]
[figure not shown]

Table 14.3.1.1.2

Summary of Treatment Emergent Adverse Events by Gabapentin and/or Pregabalin use at Baseline Safety Population

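### SAP efficacy shells for PGIC and for the supplementary responder models depart from the SAP's own rules on population, arm grouping and denominator

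*SAP*

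**What the plan says.** **General rules.** SAP Section 5 states: "The ITT population will be the primary population used for the efficacy analyses". On arm grouping, Section 3.5 says "In the efficacy outputs, subjects will be analyzed according to randomized treatment on the VMDN-003 study", and Section 6 repeats it: "All efficacy outputs will be presented by randomized treatment on the VMDN-003 study". Section 4.1 sets the denominator: "The denominator for by-visit displays will be the number of subjects in the relevant study population with non-missing data at each visit".

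**PGIC shells.** Table 14.2.5.1 is titled ITT. Its note takes percentages of the N in each column and continues: "N is the number of subjects in the safety population. Subjects are summarized by treatment received in the VMDN-003 study". The next table is titled "Summary of Patient's Global Impression of Change (PGIC) by Gabapentin and/or Pregabalin use at Baseline mITT Population". It is specified as the same shell as 14.2.5.1, with only group rows added and the CMH test and its footnote removed.

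**Responder models.** Table 14.2.3.2.1 (20% reduction) carries the title line "Tabulation of Fitted Summary Statistics from GLMM for Repeated Measures mITT Population". Tables 14.2.3.2.2 to 14.2.3.2.5 (30, 40, 60 and 70%) reuse it and are also mITT. The 50% model (14.2.2.2) and the descriptive counts at the other five thresholds (14.2.3.1) are ITT. Section 5 defines the narrower set: "The modified intent-to-treat (mITT) population will include all subjects who sign consent for the safety extension study and complete the Day 365 visit".

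**Protocol.** Section 5.5 puts the primary analyses of both primary and secondary endpoints on the safety population, by treatment received. SAP Section 10 records no changes from the planned analysis.

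**The concern.** The title and note of Table 14.2.5.1 cannot both be followed, and the note also conflicts with Sections 3.5, 4.1, 5 and 6. A programmer would have to choose the arm grouping and the denominator for a named secondary endpoint. SAP Section 13 lets only minor, cosmetic shell changes pass without modifying the SAP, and these choices are not cosmetic.

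The responder models raise a different problem. Membership of mITT depends on an event after randomisation, namely completing Day 365. Protocol 3.4.3 has subjects consent after their Day 270 assessments, so someone who consents and then misses Day 365 should already have passed the Day 90, 180 and 270 visits. A repeated-measures model restricted to mITT discards those observed scores. Section 8.1 presents the five extra thresholds as further runs of the 50% model, but the shells give the two no common population.

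**Working it through.** The documents give no PGIC rate, non-completion rate or sample size, so there is no planned figure to reproduce. All rates and counts below are assumptions.

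**1. Labels side by side**

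| Output | Population in title | Arm grouping in note |
|---|---|---|
| 14.2.5.1 PGIC overall | ITT | received (N = safety) |
| 14.2.5.2 PGIC by stratum | mITT | inherits 14.2.5.1 |
| 14.2.2.2 model, 50% | ITT | randomised |
| 14.2.3.1 counts, 20/30/40/60/70% | ITT | randomised |
| 14.2.3.2.1 to 14.2.3.2.5 models, same five thresholds | mITT | randomised |

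**2. Safety versus ITT.** Safety is everyone who consents to the extension. ITT is everyone who consents and was randomised in VMDN-003. Inclusion criterion 1 requires randomisation, and the ITT definition does not remove screen failures. The two sets are therefore practically identical.

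**3. PGIC denominator.** Let f be the share of consenters without a PGIC. Dividing by column N (safety or ITT) gives

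printed rate = assessed rate × (1 - f).

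- Assessed rate 30%: f = 10% gives 30 × 0.90 = 27.0%; f = 15% gives 30 × 0.85 = 25.5%; f = 20% gives 30 × 0.80 = 24.0%.
- Assessed rate 40%: f = 0, 5, 10 and 20% gives 40.0, 38.0, 36.0 and 32.0%, a gap of 0, 2, 4 and 8 points.

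PGIC in this study is collected only at Day 365. Under the non-missing rule in Section 4.1, the ITT and mITT percentages therefore coincide, and the gap disappears.

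**4. CMH test.** Subjects without a PGIC contribute nothing to the test, so ITT and mITT give essentially the same p-value. Only the choice between randomised and received treatment could move it.

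**5. Arm grouping.** Assume 50 per arm, with 15 improved on placebo and 25 on VM202 (30.0% versus 50.0%). Suppose k improved subjects randomised to placebo received VM202. Grouping by treatment received gives (15 - k)/(50 - k) versus (25 + k)/(50 + k):

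- k = 0: 30.0% versus 50.0%, no change
- k = 1: 14/49 = 28.6% versus 26/51 = 51.0%
- k = 3: 12/47 = 25.5% versus 28/53 = 52.8%

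**6. Responder models.** Let d be the share of consenters who do not complete Day 365. Assume crude Day 90 response of 40% in completers and 20% in non-completers. The mITT rate is 40.0%. The ITT rate is 40 × (1 - d) + 20 × d, which is 39.0, 38.0 and 36.0% for d = 5, 10 and 20%. If non-completers respond equally, both rates are 40.0%.

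**The case against.** The strongest objection is that the PGIC note agrees with the Protocol. Section 5.5 asks for the safety population by treatment received, so it is the SAP's ITT rule that departs. This stands, and it means that editing the shells alone is not enough. It does not rescue the SAP, whose own title and Sections 3.5, 5 and 6 still contradict the note.

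Second, Section 4.1 also has a general rule that percentages use the whole population in each arm, and the note could be read as applying it. But the PGIC shell is laid out by study visit, with a Day 365 row, so the more specific by-visit rule applies. At the least, the SAP should say which one governs.

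Third, naming ITT as primary does not forbid mITT analyses, and Section 8.1 names no population for the extra thresholds. That is correct. The fault is narrower: those five models have no ITT version. Their shells do specify randomised treatment, so the arm-grouping problem does not reach them.

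Fourth, the Protocol calls the analyses descriptive, SAP Section 3.2 disclaims power, and the extra thresholds are not named endpoints. This limits the severity but does not remove the contradiction.

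**Conclusion.** The inconsistency is real; its severity is minor to moderate. Followed literally, the PGIC note counts missing assessments in the denominator and groups a randomised comparison by treatment received. The five supplementary responder models leave out observed earlier data of later non-completers. The denominator effect is 3 to 6 points on a 30% rate if 10% to 20% of consenters lack a PGIC. That share is assumed, and with none missing the effect is zero. The responder-model effect depends on how many subjects miss Day 365 and on whether they respond differently.

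A reader might infer more than the documents support:

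- **That safety N exceeds ITT N because of screen failures.** The definitions make the two practically the same people.
- **That the overall PGIC rate would fall below both stratum rates.** This needs the stratum table to use mITT or non-missing denominators. Table 14.2.5.2 inherits the column-N, safety-population note, so which denominator it would use is unresolved.
- **That a responder curve would join points from two populations.** Neither document plans such a curve, and the descriptive counts at all six thresholds are ITT.
- **That the randomised comparison is already broken.** Nothing in the documents indicates that anyone was mis-dosed.

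**What to change.** 1. Set Tables 14.2.5.1 and 14.2.5.2 to ITT by randomised treatment. Base percentages on subjects with non-missing PGIC, add a row for missing, and rewrite the note accordingly.
2. Run Tables 14.2.3.2.1 to 14.2.3.2.5 in ITT and keep the mITT versions as sensitivity analyses.
3. Reconcile Protocol 5.5 with the SAP's ITT rule for efficacy, and record the departure and its reason in SAP Section 10.

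The cost is a few shell edits, five additional ITT model runs on data already planned for collection, and one entry in Section 10. It should be done before unblinded analysis, since the SAP presents itself as an a priori plan.
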